5. TREATMENT OF SUBJECTS

5.1 Investigational product/treatment

Patients with an established perianal fistula and a seton in situ or for which a new seton will be placed will be included in the study.

All patients start with the placement of the SuperSeton at the outpatient clinic or at the operating theatre in day care setting. The flow chart is demonstrated in the attached figure 1 (Appendix). After 3 months, the feasibility of the SuperSeton will be assessed.

The SuperSeton is made of medical grade Polyurethaan, which is widely already used in clinical practice as catheters (instech BTPU 027). The setons including the insert (BTPU) are delivered sterile (Synergy Health). Therefore, there is no additional risk associated with SuperSeton placement.

6. METHODS

6.1 Study parameters/endpoints

6.1.1 Main study parameter/endpoint

- The primary outcome is seton failure (loosening of the seton)

6.1.2 Secondary study parameters/endpoints (if applicable)

- Procedure time
- Complications
- Disease activity and quality of life, as measured with the Perianal Disease Activity Index (PDAI) score

6.2 Study procedures

Informed consent will be obtained at the outpatient department in all eligible patients by the study team. Seton replacement will be performed at the outpatient clinic and new setons will be placed at the operating theatre in day care setting. All patients will be followed for 3 months by the study team. The flow chart is provided in the attached figure 1 (Appendix).

Patients will be contacted by telephone after \pm 3 months the study coordinator to assess complications, additional interventions, re-admissions, duration of hospital stay and visits to the outpatient clinic.

6.3 Questionnaires

The following questionnaire will be used:

PDAI score: The Perianal Disease Activity Index (PDAI) is the gold standard for evaluating the severity of perianal disease. It includes five items: discharge, pain, restriction of sexual activity, type of perianal disease, and degree of induration. Each category is graded on a 5-point Likert scale ranging from no symptoms to severe symptoms.

6.4 Withdrawal of individual subjects

Patients can leave the study at any time for any reason if they wish to do so without any consequences. The investigator can decide to withdraw a subject from the study for urgent medical reasons.

SAFETY REPORTING

6.5 Section 10 WMO event

In accordance to section 10, subsection 4, of the WMO, the sponsor will suspend the study if there is sufficient ground that continuation of the study will jeopardise subject health or safety. The sponsor

will notify the accredited METC without undue delay of a temporary halt including the reason for such an action. The study will be suspended pending a further positive decision by the accredited METC. The investigator will take care that all subjects are kept informed.

6.6 Adverse and serious adverse events

Adverse events are defined as any undesirable experience occurring to a subject during a clinical trial, whether or not considered related to the investigational procedure. All adverse events reported spontaneously by the subject, or observed by the investigator or his staff will be recorded.

A serious adverse event is any untoward medical occurrence or effect that

- results in death;
- is life threatening (at the time of the event);
- requires hospitalisation
- results in persistent or significant disability or incapacity;
- is a new event of the study likely to affect the safety of the subjects, such as an unexpected outcome of an adverse reaction, lack of efficacy of an IMP used for the treatment of a life threatening disease, major safety finding from a newly completed animal study, etc.

An *adverse reaction* (AR) is an untoward and unintended response to the investigational product(s) related to any dose administered.

A *suspected serious adverse reaction* (SSAR) is a serious adverse reaction, of which the nature, or severity, is consistent with the applicable product information i.e. the summary of the product characteristics.

A *suspected unexpected serious adverse reaction* (SUSAR) is a serious adverse reaction, of which the nature, or severity, is not consistent with the applicable product information i.e. the summary of the product characteristics.

Reporting procedure applies to all (S)AE's occurring from the time a subject gives consent until 30 days after the last study medication administration and to any SAE that occurs after the 30-day period, if it is considered to have a reasonable possibility to be related to the protocol treatment or study participation.

A life threatening SAE, or SAE with death as a result, must be reported within 7 days after the local investigator has been informed. Other SAEs must be reported within 15 days.

The study coordinator is responsible for reporting SAEs at CCMO module ‘ToetsingOnline’. Using the CCMO module ‘ToetsingOnline’, all SAEs will be reported to the CCMO and central METC. By means of this website notifications will be sent to the relevant authorities (METC/LAREB/EudraVigilance). The reporting will occur within 15 days after the investigator has first received information on the SAE. For fatal or life-threatening cases a preliminary report will be offered within 7 days followed by a complete report within 8 days.

The following SAE’s do not require immediate reporting but will be reported once yearly in line-listings to the accredited METC that approved the protocol:

- Elective hospitalization for pre-existing conditions that have not been exacerbated by trial treatment
- A hospitalization which was planned before the subject consented for study participation and where admission did not take longer than anticipated
- Social and/or convenience admission to a hospital
- Disease recurrence in the follow-up period requiring hospitalisation

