1.1 Introduction & rationale

Perianal fistulising disease is associated with local pain, discharge, and considerable morbidity rates (including sphincter and perineal tissue destruction) resulting in a negative impact on quality of life.¹ The main cause of perianal fistula development is sepsis originating from the cryptoglandular glands.² Other aetiologies are Crohn's disease (CD), malignancies, radiation, trauma or foreign bodies. In simple or low fistulas (lower one-third of the external sphincter) treatment consists of lay open techniques and recurrences are hardly seen.

In contrast, complex or high perianal fistulas (upper two-third of the external sphincter) have limited treatment options. The most frequently used treatment approach has been surgical non-cutting seton placement for chronic drainage of the fistula. This technique dates back to the ancient times. A seton maintains patency of the tract and eliminates the accumulation of pus which prevents the recurrent formation of tracts and abscesses. In addition, fibrosis of the fistula tract can be achieved.

However, the seton has been reported to negatively influence quality of life and is associated with a decreased Perianal Disease Activity Index (PDAI score).³ Closure rates after seton removal vary widely in patients with CD (13.6%-100%).⁴ Nowadays, vessel loops or sutures are used as seton to drain the fistula. The ends of the seton drain are connected by a knot or a suture according to known methods. A knotted seton is relatively difficult to clean, and the knot has a tendency to rotate towards the external opening of the fistula tract and sometimes even migrate in to the fistula tract. This may cause complaints of pain and discomfort. This matter is widely discussed on patient forums. Last year, a survey regarding complaints of the knot of the seton, was send via the website of the CCUVN (Crohn en Colitis Ulcerosa Vereniging Nederland) to patients with perianal fistulas. This survey showed that complaints varied from irritation, discharge of blood and/or pus, pain and itching. Sitting and bicycling were mentioned as activities that aggravated the symptoms. Up till now one other knotless seton is available, the Comfort Drain.⁵

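### Section 6.6 defers hospitalised disease recurrence to a yearly METC listing with no relatedness or severity condition, so a recurrence after drain failure could miss prompt reporting

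*Protocol*

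**What the plan says.** Section 6.6 sets a general rule: SAEs go to the CCMO and the METC within 15 days, and for the gravest events "A life threatening SAE, or SAE with death as a result, must be reported within 7 days". It then lists four kinds of SAE that are exempt from immediate reporting and go to the METC once a year. The fourth is "Disease recurrence in the follow-up period requiring hospitalisation".

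The first two items are limited. One reads "Elective hospitalization for pre-existing conditions that have not been exacerbated by trial treatment". The other covers admissions planned before consent, and only "where admission did not take longer than anticipated".

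The default reporting window for (S)AEs runs from consent "until 30 days after the last study medication administration". After that, an SAE stays reportable if it may be related to the protocol treatment or to participation. The treatment itself is a drain: "All patients start with the placement of the SuperSeton at the outpatient clinic or at the operating theatre in day care setting" (section 5.1).

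**The concern.** In this trial, recurrence is not clearly separate from the performance of the device. Section 1.1 says that a seton "prevents the recurrent formation of tracts and abscesses", and section 6.1.1 makes loosening of the seton the primary outcome. If a drain loosens or is lost and the tract or abscess then recurs, an admission for it may be a consequence of device failure. That is an event an ethics committee would want to hear about promptly. The recurrence item has no wording that keeps such a case on the 15-day route.

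At stake is the timing of notice to the METC, which bears on any decision to suspend the study under section 6.5. There is no DSMB (section 6.8), so the METC is the main body outside the study organisation that could react.

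The window raises a smaller question: it is tied to an event that never occurs in a trial without study medication.

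**Working it through.** No stated figure needs to be reproduced. The check compares the rules with one another and adds simple arithmetic on timing.

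1. **Conditions within the exemption list (section 6.6).**
   - Elective admission for a pre-existing condition: limited to conditions that trial treatment has not made worse.
   - Admission planned before consent: limited to stays of the expected length.
   - Social or convenience admission: non-medical by description, so it needs no limit.
   - Disease recurrence with admission: no limit on relatedness, severity or length of stay.

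2. **Meaning of the term.** The protocol does not define disease recurrence. Section 6.1 lists seton failure and complications as outcomes, but nothing says whether an abscess or new tract after loosening is a complication, a recurrence or both. The item can therefore capture a device-related admission; the text does not settle whether it does.

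3. **Precedence.** Section 6.6 gives 15 days in general and 7 days for fatal or life-threatening SAEs. The exemption list gives yearly reporting. Section 6.6.1 sends SUSARs electronically through ToetsingOnline, with no timeline of its own. No sentence ranks these three. A life-threatening recurrence with admission meets both the 7-day rule and the exemption.

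4. **Timing of a yearly listing.** Inclusion takes 10 months (section 3) and follow-up 3 months (section 6.2), so the last follow-up ends at about 10 + 3 = 13 months. The protocol does not say when the reporting year starts. If it starts at first inclusion (assumption), the first listing is due at month 12, which is 12 − 10 = 2 months after enrolment closes. A year counted from an earlier date would bring the listing forward. The safety report in section 7.9 does not fill the gap, because it is submitted after the trial is complete.

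5. **The window anchor.** Take 3 months as about 91 days.
   - Anchor read as placement (assumption): the window closes at day 30, and 30/91 = 33% of follow-up is covered. The other 91 − 30 = 61 days lie outside it, except for SAEs judged possibly related.
   - Anchor read as removal or loss of the drain on day d (assumption): the window closes at day d + 30. All 91 days are covered when d is at least 61, and the window runs past 3 months when d exceeds 61 or the drain is still in place at 3 months.
   - The text does not choose between these. They are shares of follow-up time, not of events missed.

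**The case against.** The strongest reply is that several safeguards remain, and most of it stands:

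- **Recording is not affected.** Section 6.6 states: "All adverse events reported spontaneously by the subject, or observed by the investigator or his staff will be recorded". Re-admissions are collected at about 3 months (section 6.2), and all SAEs go to the steering committee (section 6.8). Only the timing of METC notice is in question.
- **The 7-day rule may survive the exemption.** Section 6.6 treats life-threatening and requiring admission as separate criteria for seriousness, and the recurrence item names only admission. It can fairly be read as relaxing the 15-day rule for events that are serious only through admission. A reader might infer that life-threatening recurrences are definitely diverted to the yearly list. The text does not support that; it only fails to say which rule wins.
- **SUSARs keep their own route.** This is a real safeguard but an incomplete one. An expected recurrence would not qualify, and section 6.6 defines reactions by dose and by a summary of product characteristics, which fit a drain poorly.
- **The drug anchor is template wording with little effect.** This is accepted. However the anchor is read, later SAEs judged possibly related stay reportable, so any gap holds only SAEs judged unrelated and non-serious AEs. It would be wrong to conclude that two thirds of follow-up goes unobserved.

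Two other strong readings also fail. One is that every admission after drain failure falls under the exemption; because the term is undefined, such events could be classed there, no more. The other takes the share of drains allowed to fail under the 70% feasibility criterion (section 4.4) as the number of patients affected. That criterion counts drains, and the documents do not say how many failures would lead to admission.

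**Conclusion.** The point holds as a defect in a stated reporting rule. An unconditional and undefined exemption covers a type of event that this device is meant to prevent, and its order of precedence against the 7-day and SUSAR rules is not given. Followed as written, it could delay METC notice of a device-related admission from 15 days to a yearly listing, possibly until after the 10-month accrual has ended. That last step assumes that the year starts at or near first inclusion. The number of patients concerned cannot be derived from the protocol.

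The medication-based window is a minor second point: the anchor is wrong for this trial, but the effect is small. Neither point touches an endpoint, the sample size or the analysis. The correction should be made because it is cheap and the trial has no DSMB.

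**What to change.** **Exemption list, section 6.6.** Limit the fourth item to recurrences with admission that are not fatal or life-threatening and have no reasonable possibility of a relation to the SuperSeton, including its loosening or loss. All others then follow the 15-day and 7-day timelines already in the section. Add one sentence stating that the 7-day rule and the SUSAR route of section 6.6.1 prevail over the list.

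**Reporting window, section 6.6.** Replace the medication anchor with one that exists in this trial and covers at least the full 3-month follow-up. Do not simply end the window at 3 months: if the present anchor is read as removal or loss of the drain, that would shorten cover for drains removed or lost after about day 61 and for those still in place. Adjust the later reference to the 30-day period to match, and keep the clause for later SAEs judged possibly related.

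**Cost.** A few sentences of text and some additional individual SAE reports to the METC; the documents give no basis for a number. Recurrences that are unrelated and neither fatal nor life-threatening stay in the yearly listing.

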6.6.1 Suspected unexpected serious adverse reactions (SUSAR)

SUSARs will be electronically reported via ToetsingOnline and the trial coordinator will communicate all SUSARs to the independent monitor and to the steering committee ([name] and [name]) of this study.

6.7 Follow-up of adverse events

All adverse events will be followed until they have abated, or until a stable situation has been reached. Depending on the event, follow up may require additional tests or medical procedures as indicated, and or referral to the general physician or a medical specialist.

6.8 Data and safety monitoring and Data Safety Monitoring Board (DSMB)

This study is considered a low risk trial. Therefore no DSMB will be installed. The AMC study coordinator will monitor the data.

Furthermore, to keep insights in SAE’s, the trial coordinator will communicate all SAE’s to the steering committee ([name] and [name]) of this study. The steering committee will comment on the reports.

STATISTICAL ANALYSIS

6.9 Statistics

All data will be collected in an electronic database by the AMC study coordinator. The outcome parameters will be analysed after 3 months follow up with appropriate statistical tests using the statistical program SPSS. A two-tailed $p < 0.05$ is considered statistically significant. Descriptive statistics will be used to describe patient characteristics and outcomes. Preoperative PDAI scores will be compared to postoperative PDAI scores after 3 months follow up. Results will be analysed using the paired t -test.

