Intervention: The SuperSeton will be placed at the outpatient clinic in patients that already have a seton in situ. This seton will then be exchanged by the SuperSeton. In case patients do not have a seton in situ, the SuperSeton can be placed at the operating theatre in day care setting instead of a regular seton.

Main study parameters/endpoints: The primary outcome is seton failure (loosening of the seton). Secondary outcomes are time of procedure, complications and quality of life measured by the PDAI ('Perianal Disease Activity Index').

Nature and extent of the burden and risks associated with participation: The SuperSeton will be placed in patients with perianal fistulas (ever) treated with a conventional knotted seton. There are no additional risks involved. The seton will be placed at the outpatient clinic in patients with a seton in situ, or at the operating theatre in day care setting in patients with a perianal abscess without a seton. The material that is used for the Setons is of medical grade polyurethane, this is the same material of catheters that are already used in clinical practice (instech BTPU 027). The Setons including the insert (BTPU) are supplied sterile (Synergy Health). **Sample size calculation:** A group of 60 patients will be included to determine feasibility of the SuperSeton. The proposed treatment protocol is considered feasible if at least 70% of the SuperSetons stay in place.

PARTICIPATING CENTRES

Surgeon

Academic Medical Center

[name]

[name]

Proctos Kliniek

[name]

INTRODUCTION AND RATIONALE

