3. STUDY DESIGN

The design of the study is a feasibility study with SuperSeton placement in patients with perianal fistulas. The trial will be conducted in the AMC and the Proctos Kliniek. Patients fulfilling the inclusion criteria without any exclusion criteria will be included in the study. The total inclusion is scheduled to take place within 10 months.

Patients will be seen at the outpatient clinic 3 months after SuperSeton placement by the surgeon. Other visits will be scheduled on indication. During these contacts the PDAI score will be assessed. Patients will be followed by the research resident to assess complications or re-admissions.

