4. STUDY POPULATION

4.1 Population (base)

Patients with a perianal fistula for which a seton was already placed in day care setting (that is still in situ) and patients presenting with a recurrent perianal fistula (ever treated with a knotted seton) for which a new seton will be placed are eligible.

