4.2 Inclusion criteria

- ≥ 18 years
- Written informed consent
- Perianal fistula with a seton in situ or a recurrent perianal fistula for which a new seton will be placed

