4.4 Sample size calculation

The sample size calculation is based on a clinically relevant decrease in the PDAI and number of re-interventions. The PDAI has 5 items, subdivided in a 5-point Likert scale (range 0-20). A score of >7 is considered as serious perianal disease. The CCUVN survey indicated that the PDAI reflected severe complaints in Crohn's fistula patients, with high scores on all 5 scales (average 9.2). A decrease to 6.9 is considered to be clinically relevant (<7 considered as moderate perianal complaints). In the survey it also became apparent that 50% required re-interventions related to the knot. Reducing the 50% of reinterventions to 30% is considered clinically important and can be expected due to the stronger insert connection and less knot-related complaints.

The sample size needed to demonstrate superiority of the SuperSeton with a significant decrease in PDAI and number of re-interventions is 60 patients (alpha 0.05, power 90%, and 5% drop-out).

Feasibility:

The proposed treatment protocol is considered feasible if at least 70% of the SuperSetons stay in place.

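### Section 4.4 sizes the trial to prove the SuperSeton superior, but a single group compared with its own baseline and a survey figure cannot show that

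*Protocol*

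**What the plan says.** Protocol section 4.4 states: "The sample size needed to demonstrate superiority of the SuperSeton with a significant decrease in PDAI and number of re-interventions is 60 patients". Its inputs are a mean PDAI of 9.2 from a patient survey falling to 6.9, a survey re-intervention rate of 50% falling to 30%, alpha 0.05, power 90% and 5% drop-out. A separate line sets the feasibility rule at 70% of SuperSetons staying in place.

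Section 3 states: "The design of the study is a feasibility study with SuperSeton placement in patients with perianal fistulas". Section 5.1 has every patient start with SuperSeton placement, and no comparison group is described. The primary outcome (6.1.1) is seton failure. PDAI is secondary, listed in 6.1.2 as "Disease activity and quality of life, as measured with the Perianal Disease Activity Index (PDAI) score".

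Section 6.9 states: "Preoperative PDAI scores will be compared to postoperative PDAI scores after 3 months follow up". The test is a paired t-test at two-tailed 0.05. No test is named for re-interventions, which 6.2 collects by telephone at about 3 months.

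Section 4.2 admits "Perianal fistula with a seton in situ or a recurrent perianal fistula for which a new seton will be placed", and 4.1 confirms that "patients presenting with a recurrent perianal fistula (ever treated with a knotted seton) for which a new seton will be placed are eligible". Section 6.2 separates the two routes: "Seton replacement will be performed at the outpatient clinic and new setons will be placed at the operating theatre in day care setting". The Summary describes the second route as placement "at the operating theatre in day care setting in patients with a perianal abscess without a seton".

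**The concern.** Superiority is a statement about one treatment against another. Here the other treatment would be a knotted seton, and no patient is followed on one. A fall in PDAI from baseline also contains time effects and regression to the mean. In patients without a seton at baseline it contains the effect of being drained at all. A re-intervention rate below 50% compares trial patients with survey respondents over a period that may differ.

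If 4.4 stands, a significant PDAI fall or a low re-intervention rate could be reported as the superiority that the trial was sized to prove, although neither result separates the knotless design from the other explanations.

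**Working it through.** **1. What the figure of 60 corresponds to.** Evaluable patients: 60 × 0.95 = 57.

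- Re-interventions, 30% against a fixed 50%, two-sided 0.05, 90% power, variance taken at 30%: (1.960 + 1.282)² × 0.21 / 0.20² = 55.2, so 56; 56 / 0.95 = 58.9, so 59.
- The usual one-sample formula: (1.960 × 0.5 + 1.282 × √0.21)² / 0.20² = 61.4, so 62; 62 / 0.95 = 65.3, so 66.
- Two concurrent arms at 50% and 30%: 124 per arm, 248 in total; 248 / 0.95 = 261.1, so 262. Sixty patients split 30:30 would have about 35% power.
- PDAI: the difference is 9.2 − 6.9 = 2.3. No SD is given, so the figure cannot be reproduced. With 57 pairs, 90% power implies an SD of change of about 5.3.

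For the re-intervention rates, about 60 is reached only as a single group against a fixed number, not as a comparison with a control. The reference in 7.6 to randomised patients does not fit the rest of the protocol and describes no second arm.

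**2. What each comparison contrasts.**

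| Comparison | Contrast | Also contained in the difference |
|---|---|---|
| PDAI, seton exchanged | old seton, then SuperSeton | time, regression to the mean |
| PDAI, no seton at baseline | undrained fistula, then SuperSeton | the same, plus drainage by any seton |
| Re-interventions | SuperSeton over 3 months, against survey 50% | different patients, unstated survey period |

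No row compares the SuperSeton with a concurrent knotted seton.

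**3. Illustration for PDAI.** The share without a seton (f), the drainage fall (e) and the SD within groups (s) are all assumed. With no device effect, mean change = f·e and SD = √(s² + f(1−f)e²). Example: f = 0.25, e = 4, s = 5 gives mean 1.0 and SD √(25 + 3) = 5.29. The two-sided paired t-test on 57 pairs (noncentral t) is then significant in 28.9% of trials.

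| f | e | s = 4 | s = 5 | s = 5.3 |
|---|---|---|---|---|
| 0.10 | 2 | 6.6% | 6.0% | 5.9% |
| 0.10 | 4 | 11.0% | 8.9% | 8.5% |
| 0.25 | 2 | 14.8% | 11.3% | 10.6% |
| 0.25 | 4 | 39.8% | 28.9% | 26.5% |
| 0.50 | 2 | 43.6% | 30.7% | 28.0% |
| 0.50 | 4 | 91.3% | 78.7% | 74.5% |

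**4. Splitting the groups does not rescue superiority.** Take an assumed 40 exchange pairs and no device effect. A non-device fall of 0.5 point is significant in 12.0 / 9.5 / 9.0% of trials at SD 4 / 5 / 5.3, and a fall of 1 point in 33.8 / 23.5 / 21.4%.

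**5. Re-interventions.** An exact two-sided binomial test against 50% with 57 patients is favourable at 20 or fewer events. Suppose the SuperSeton changes nothing. If the true 3-month rate is 50%, the chance of a favourable result is 1.7%. If it is 45%, because the survey covered a longer period or different patients, the chance is 8%. At 40% it is 27%.

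**The case against.** The strongest reply is that this is one phrase in a feasibility protocol. Sections 2 and 3 speak of feasibility, PDAI is secondary, the only decision rule is the 70% threshold, and 6.9 does not mention superiority. That stands, and it limits the consequence. It does not remove the sentence, which is the stated basis for the sample size.

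A second reply is that the SAP may split the analysis by baseline seton status. That also stands: 6.9 describes one comparison and names no split, but it does not say that the groups are pooled, so pooling is an inference. No SAP can supply the missing control, and step 4 shows that the superiority reading fails even with a split.

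Third, needing both results might seem to protect the claim, since a joint success could be no more frequent than the 1.7% in step 5. Section 4.4 does not say that both must succeed, and that cap holds only at a true rate of exactly 50%.

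A reader might also infer that the paired t-test is the wrong test. It is valid for mean change; the fault is the meaning that 4.4 attaches to it.

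**Conclusion.** The point holds for section 4.4: neither stated comparison can establish superiority over a knotted seton. This follows from the design and needs no assumed figure.

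The size for PDAI does rest on assumptions. The protocol gives no SD, no share of patients without a seton and no drainage effect, so the 6% to 91% range is an illustration. It should not be read as the trial's false-claim rate. Bias in favour of the device is likely but not certain: section 1.1 says that setons clear pus and links them to a decreased PDAI, yet in the same sentence reports worse quality of life.

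A reader might go further and conclude that the feasibility result is compromised. The documents do not support that, because the 70% rule uses neither PDAI nor re-interventions. The correction should be made, but its reach is limited to the superiority statement and the reading of two results.

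**What to change.** In 4.4, replace the superiority clause with: *detect a within-patient before/after decrease in PDAI and a re-intervention rate below the 50% survey benchmark*. Then add: *Without a concurrent control neither result establishes superiority over a knotted seton.* This covers both outcomes, since both are uncontrolled.

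In 6.9, keep the overall paired t-test as a test of mean change. Add that PDAI change is also reported separately for patients exchanging a seton in situ and for patients without a seton at baseline, and that only the exchange group is read as bearing on the change of seton.

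Restricting the t-test to exchange patients is not needed. It would cost power (for 2.3 points with an assumed 40 pairs, 94 / 81 / 76% at SD 4 / 5 / 5.3) and still could not show superiority.

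The costs are that the superiority claim is given up and that the separate estimates are less precise. At an assumed SD of 5, the standard error is 5/√57 = 0.66 overall, 5/√40 = 0.79 with 40 exchange patients and 5/√28 = 0.94 with 28. No extra patients or visits are needed.
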